9. SAFETY MEASUREMENTS

Collecting, Recording and Reporting of Adverse Events

An adverse event is any unfavorable and unintended sign, symptom, or disease temporally associated with the use of medical treatment or procedure that may or may not be considered related to the medical treatment or procedure.

Outcomes of this comparative effectiveness trial include data collection of adverse events. Adverse events include pneumonia and other ventilator-associated events, including acute care transfers due to respiratory complications, pneumothorax, transfer to acute care hospital due to respiratory complications, weaning failure, new pneumothorax, acute respiratory distress syndrome, pleural effusion, pulmonary embolism, atelectasis, and pulmonary edema.

The Investigators/ RA will be responsible for collecting and reporting adverse events during the trial. The investigators/ RA will collect adverse events related to the randomized control trial.

The PI will report problems according to the UTHSC-Houston IRB policy, specifically in the event which in the opinion of the PI is both unexpected and related and places subjects or others at risk of harm.

An adverse event is any unfavorable and unintended sign, symptom, or disease temporally associated with the use of medical treatment or procedure that may or may not be considered related to the medical treatment or procedure.

Outcomes of this comparative effectiveness trial include data collection of adverse events. Adverse events include pneumonia and other ventilator-associated events, including acute care transfers due to respiratory complications, pneumothorax, transfer to acute care hospital due to respiratory complications, weaning failure, new pneumothorax, acute respiratory distress syndrome, pleural effusion, pulmonary embolism, atelectasis, and pulmonary edema.

The Investigators/ RA will be responsible for collecting and reporting adverse events during the trial. The investigators/ RA will collect adverse events related to the randomized control trial.

The PI will report problems according to the UTHSC-Houston IRB policy, specifically in the event which in the opinion of the PI is both unexpected and related and places subjects or others at risk of harm.

AEs and Reportable Events will be recorded. AE will be recorded on the appropriate case report form (CRF) page from the time written informed consent is obtained until completion of the study or until resolution of the reportable event. Information to be collected includes the description of the AE, date and time of onset, severity, duration, causality, outcome, and relationship to the study procedure. If an AE is assessed by the I

UTHealth
Houston

IRB NUMBER: HSC-MS-21-0222
as not reasonably
IRB APPROVAL DATE: 02/23/2023

attributable to study intervention, its occurrence must also be recorded in the source documents and reported on the CRF.

Safety Monitoring Plan

The Data Safety Monitoring Plan (DSMP) for the research study includes statistical analysis on rates of morbidity of study participants compared to controls by the PI and the statistician at 50% recruitment stage. If preliminary results suggest the risk of pneumonia is <25% in one group compared to another group, we will stop the study.

We will follow standard clinical procedures in the event of a desaturation episode. The most common cause of desaturation is a mucus plug in people with spinal cord injury in the rehabilitation setting. We will first suction the patient. If a patient is still not improving with suctioning, we will adjust ventilator settings, including tidal volume, to address clinical needs. Given that we have a range of VT in each group, we will first adjust within that range if VT has to be adjusted. If a person requires further adjustment in VT, we will allow the changes in ventilator settings to meet the patient's needs. We will not remove any patient from the study. We will include this data for intent to treat analysis. However, this event will be considered a treatment failure, and data will be included to calculate feasibility metrics for a larger study.

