3. STUDY POPULATION

Sample Size: We plan to recruit 45 subjects (15 in low Vt, 15 in high Vt, and 15 in the control group). We will recruit 30 adults with acute cervical SCI admitted on mechanical ventilation from TIRR MHH and Craig Hospital and an additional 15 people with acute cervical SCI not dependent on mechanical ventilation at admission to serve as controls from TIRR MHH.

Criteria for Recruitment: All consecutive patients with SCI admitted to TIRR MHH and Craig Hospital will be screened for eligibility based on inclusion and exclusion criteria during the study period. The screening will involve the review of history from the patient or primary admitting clinician. If a patient meets eligibility criteria, the research coordinator will provide further information on the study, answer any questions, and recruit if they are willing to participate and provide consent.

Inclusion Criteria: Subjects must meet all of the inclusion criteria listed below to participate in this study.

- Adult patients \geq 18 years (Lung volumes and ventilator settings are different for ages <18 years).
- Acute SCI of duration \leq four months
- Mechanical ventilation subjects: traumatic or non-traumatic cervical SCI with neurological level C1-C5 admitted to our acute inpatient rehabilitation facility (AIR) on mechanical ventilation.
- Control subjects: traumatic cervical SCI admitted to our acute inpatient rehabilitation facility (AIR) who are not dependent on mechanical ventilation.

Exclusion Criteria: All subjects meeting any of the exclusion criteria listed below at baseline will be excluded from participation.

- Severe dysphagia due to concomitant brain stem injury, which increases the risk of pneumonia
- Severe brain injury resulting in dysphagia and inability to follow instructions to perform vital capacity measurements
- ARDS or severe lung disease (required supplemental oxygen or ventilator prior to SCI) at the time of admission (these conditions will not allow patients to randomize because target Vt may below)
- Prolonged antibiotics for > 3 weeks at the time of admission due to infection (e.g., osteomyelitis, epidural abscess, etc.),
- Presence of diaphragmatic pacemaker.

Withdrawal Criteria: Possible reasons for discontinuation of study intervention: Intolerance to proposed ventilator settings.

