6. METHODS AND ASSESSMENTS

Intervention: Lower Vt group will be kept 8- 10 ml/kg pbw with PEEP, and in the high Vt group, the participant will receive a tidal volume of 14-16 ml/kg pbw with PEEP. The PEEP will be adjusted based on atelectasis on X-ray findings and patient tolerance within 5-10 cm H₂O range. These thresholds are used based on our cohort study²⁶ and survey data, which suggest the current median minimum to maximum Vt range used in rehabilitation hospital setting ranges from 8-16 ml/kg pbw. Tidal volumes will be increased per our institutional protocol at a rate of 50-100 ml per day until the target range is achieved. All participants at admission will be switched to Assist Control (AC) Mode or synchronized intermittent mandatory ventilation which is the current standard of practice in our free-standing acute inpatient rehabilitation unit. We will monitor peak and plateau pressures. All study participants will receive standard respiratory care, including secretion management using sub-glottic suction, mechanical insufflator-exsufflator, albuterol-ipratropium nebulization as-needed medications for thick secretions (e.g., N-acetylcysteine, guaifenesin).

Ventilator weaning Protocol is managed by board-certified SCI medicine rehabilitation physicians in our institution. Internal Medicine physicians are consulted on all our mechanically ventilated patients, and pulmonologists are available for consultation as needed. The ventilator

weaning protocol begins once the patient is determined to be medically stable by the attending physician and satisfies the following institutional criteria: lung auscultation with clear or relatively clear breath sounds, vital capacity >10-12 ml/kg pbw measured by Wright's spirometer via mouth or tracheostomy, chest X-ray clear or stable, arterial blood gas analysis on room air within normal limits, no active infection, hemoglobin >10 gm/deciliter and should be tolerating tracheostomy cuff deflation. The institutional weaning protocol consists of 12-19 days of progressive ventilator-free spontaneous breathing. The weaning schedule is adjusted sometimes due to respiratory complications, anxiety, and inability to tolerate protocol.

Control group: Both controls and people in mechanical ventilation groups will receive standard comprehensive inpatient rehabilitation services, including physical therapy, occupational therapy, speech, and respiratory therapy if needed.

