Consent: If a subject agrees to participate, then they will be given an IRB-approved consent form to review and sign. There will be separate consent forms for MV group and controls due to different risks and procedures involved for participation in respective group. Those with tetraplegia will unlikely have the ability to sign and we will have a third-party attest to the consent. Because of the study's time constraints, they will have 1 day to decide upon whether they will participate.

Study procedures for MV group:

Day 0-1: screen, approach for informed consent
Day 1-2: obtain consent and randomization
Day 1-2: Baseline blood and tracheal specimen for inflammatory marker analysis
Day 1-4: Titrate tidal volume to achieve respective targets in each group
Day 4-6: 2nd blood and tracheal specimen (within 48 hrs after achieving target Vt)
Days 14-18: 3rd sample (post-weaning or 2-week sample)
Day 0- Discharge: Adverse events monitoring and outcome data collection

Study procedures for control group:

Day 0-1: screen, approach for informed consent
Day 1-2: obtain consent
Day 1-2: Baseline blood specimen for inflammatory marker analysis
Days 14-18: 2nd sample (2-weeks from baseline)
Day 0- Discharge: Adverse events monitoring and outcome data collection

We will collect demographics, outcome data, and adverse events from electronic medical records during their stay at TIRR (day 0- discharge).

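### The 50% morbidity review names the non-randomised, non-ventilated controls as comparator instead of comparing the two randomised tidal-volume arms

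*Combined protocol and SAP*

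**What the plan says.** Section 9, Safety Monitoring Plan, describes one interim analysis: "statistical analysis on rates of morbidity of study participants compared to controls by the PI and the statistician at 50% recruitment stage". The next sentence gives the only stopping rule: "If preliminary results suggest the risk of pneumonia is <25% in one group compared to another group, we will stop the study". It does not name the two groups. Neither sentence says whether the Vt arms are pooled or shown separately.

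Section 3 defines the comparator as "an additional 15 people with acute cervical SCI not dependent on mechanical ventilation at admission to serve as controls from TIRR MHH". The entry criteria differ between the two populations: "Mechanical ventilation subjects: traumatic or non-traumatic cervical SCI with neurological level C1-C5" on one side, "Control subjects: traumatic cervical SCI admitted to our acute inpatient rehabilitation facility (AIR) who are not dependent on mechanical ventilation" on the other. Ventilated patients come from both hospitals.

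Section 6 keeps the two populations apart: "Both controls and people in mechanical ventilation groups will receive standard comprehensive inpatient rehabilitation services", and "There will be separate consent forms for MV group and controls". Section 5 applies the 1:1 allocation to the ventilated groups only.

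For each adverse event, Section 9 records the description and "date and time of onset, severity, duration, causality, outcome, and relationship to the study procedure".

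**The concern.** Randomisation lets this trial ask whether one Vt range does more harm than the other. The question is a live one: Section 1 reports that the centre's own rehabilitation cohort had more pneumonia and more pulmonary adverse events with high Vt. The interim morbidity review, followed as worded, answers a different question, namely how ventilated patients fare against patients who need no ventilator. That gap can be wide when the two Vt ranges are equally safe. It also gives no direct reading of whether pneumothorax, ARDS, respiratory transfer or death is gathering in one arm.

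**Working it through.** **1. What the terms mean.** Sections 3, 5, 6, 8 and 11 use controls, as a group, only for the non-ventilated patients. Neither Vt arm is called a control arm. Where Sections 18-style event reporting and sample size refer to a randomised control trial (Sections 9 and 11), that names a design and not a group. Section 5 uses study participants for those randomised to high or low Vt. The literal contrast is therefore ventilated against non-ventilated.

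**2. How the two sides differ (Section 3).**

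| | Ventilated | Controls |
|---|---|---|
| Randomised | yes, 1:1 | no |
| Ventilated at admission | yes | no |
| Hospitals | two | one |
| Cause of injury | traumatic or non-traumatic | traumatic only |

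**3. Numbers at the review.** The planned total reproduces: 15 + 15 + 15 = 45. Half of the 30 ventilated patients is 15, or about 8 and 7 per arm. If the 50% refers to all 45, then 45/2 = 22.5. Section 11 expects 10 to 12 ventilated patients a year, and 15 controls in 2 years (7.5 a year). The ventilated share is then 22.5 × 10/17.5 = 12.9 to 22.5 × 12/19.5 = 13.8, giving arms of about 7 and 6, or 7 and 7.

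**4. What the named contrast shows.** The documents give no risks by arm, so all values here are assumed. Let *b* be the event risk in the safer arm, *b + d* the risk in the other arm, and *c* the risk in controls, in percentage points.

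- *Arms equally safe (d = 0):* the contrast with controls is *b − c*, which is 0, 10 or 20 points for assumed gaps of those sizes. The contrast between arms is 0.
- *Arms shown separately, d = 30:* they differ from controls by *b − c* and *b − c + 30*. Subtraction returns the full 30.
- *Arms pooled, d = 30:* the contrast is *(b − c) + w × 30*, where *w* is the harmful arm's share of ventilated patients. With 7 of 15, 0.467 × 30 = 14; with 8 of 15, 0.533 × 30 = 16.

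| *b − c* | Pooled contrast, d = 0 | Pooled contrast, d = 30 | Arm contrast, d = 30 |
|---|---|---|---|
| 0 | 0 | 14 to 16 | 30 |
| 10 | 10 | 24 to 26 | 30 |
| 20 | 20 | 34 to 36 | 30 |

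A pooled contrast of 24 points could mean *b − c* = 10 with a 30-point excess in one arm (*w* = 7/15), or *b − c* = 24 with no difference between arms. Likewise, with equal arms, assumed risks of 30%/30%, 20%/40% and 10%/50% all pool to 30%, while the risk ratios between arms are 1.0, 0.5 and 0.2. With the smaller splits in step 3, *w* runs from 6/13 to 7/13, so about half of the excess still shows.

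**The case against.** The strongest reply is that this is loose drafting. The two sentences adjoin, the second holds the only action rule, and pneumonia is both the primary outcome and the object of the randomised comparison. The rule may well be meant as arm against arm. The plan also says that monitoring includes this analysis, so other looks are not excluded. All of that stands, and it confines the point to morbidity other than pneumonia and to death. It does not change the comparison that the first sentence names.

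Second, nothing is lost if the arms are displayed side by side. That is correct. Loss of information requires pooling, which the text neither states nor rules out.

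Third, a table by arm would tell little. Under assumed risks of 15% in an arm of 7 and 5% in an arm of 8, the harmful arm shows no more events than the safer one in about 47% of looks. With 5% in both arms, 0.95^15 = 46% of looks contain no event at all. This stands as a limit on what the remedy can deliver, and is why the table should carry no trigger.

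Fourth, airway pressures are monitored (Section 6), Vt may be changed for clinical need (Section 9), and the intervention may be stopped for intolerance (Section 3). These protect the individual patient but compare nothing between arms. Aim 1 in Section 11 can report harm by arm, but states no interim use.

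**Conclusion.** The point holds in a limited form. The morbidity review states the wrong contrast: it names a confounded, non-randomised comparator where the two Vt arms belong. The practical size runs from nothing lost except a misdirected headline comparison (arms shown separately) to roughly half of any excess visible and not separable (arms pooled; 14 to 16 of an assumed 30 points). The documents do not settle which applies, and every risk used is an assumption.

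Four stronger readings are tempting and unsupported:

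- *No interim look at the arms is planned.* The pneumonia rule can be read as exactly that.
- *The plan pools the arms and so hides harm.* Pooling is nowhere stated.
- *Serious respiratory events and death fall outside the review.* Pneumothorax, ARDS and respiratory transfer plausibly count as morbidity, and death can be recovered from the recorded adverse-event outcome. What is missing is a stated split by arm.
- *The groups also differ by neurological level.* The Section 3 criteria might suggest so, but Section 11 gives C1 to C5 for controls too.

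The pneumonia rule's undefined scale, and how readily it could be met when the arms have equal risk, is a separate matter and not part of this error.

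**What to change.** Amend the Safety Monitoring Plan in Section 9 as follows.

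1. Make the 50% morbidity review a comparison of the two randomised Vt arms, labelled A and B by the research assistant who randomises, with controls as a descriptive column only.
2. At that review, tabulate by coded arm the number of patients who, after randomisation, died or had a new pneumothorax, ARDS or an acute-care transfer for a respiratory cause. Keep the table descriptive, with no new numeric trigger.

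The cost is a short amendment and one table at a review already planned. The respiratory events are already collected and death can be taken from the adverse-event outcome field, so no new data item, visit, committee, staff or patients are needed. Labelling also fits Section 6, which keeps the research assistant out of data analysis.

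There are two downsides. Coding limits but does not guarantee the blinding of the principal investigator and statistician: the investigator reviews data anomalies, the database is accessed through the investigator's computer (Section 10), and the data include Vt and airway pressures (Section 6). And with about 7 to 8 patients per arm the table is only a coarse check. Naming the arms will also make the pneumonia rule more naturally read as A against B, so its scale should be settled, as a separate item, at the same time.

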5. STUDY DESIGN

We propose a randomized comparative effectiveness trial to study systematically current Vt ranges to determine optimal settings to improve outcomes. Study participants will be randomly assigned to high tidal volume (14-16 ml/kg pbw) or low tidal volume of 8 to 10 ml/kg pbw within 48 hrs of admission. Subjects will be stratified based vital capacity at admission (≥ 5.8 cc/kg pbw) to ensure equal allocation of those with the most severe respiratory impairment and unlikely to wean from the vent. In our experience, vital capacity ≥ 5.8 cc/kg pbw was associated with higher odds of weaning. We will screen and recruit an additional 15 people with acute SCI not dependent on mechanical ventilation at admission to serve as controls. We anticipate 3 years to complete study recruitment. A 1:1 allocation ratio will be applied to the mechanical ventilation groups. Participants, principal investigator, outcome assessors, and statistician will be blinded to tidal volume assignment.

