Additional data: Additional data collection will include age, sex, weight, height, date of injury, date of admission to AIR, time since injury, mechanism of injury, American Spinal Injury Association (ASIA) impairment scale (AIS), vital capacity at admission, maximum vital capacity achieved during AIR stay, ventilator settings including Vt, peak and plateau pressure, hospital length of stay and discharge location. We will also collect information on any other ongoing or new infectious events other than pneumonia.

Randomization: Each subject will be randomized to either a tidal volume of 8-10 ml/kg pbw or 14-16 ml/kg pbw within 48 hrs of admission after obtaining consent. A 1:1 allocation ratio will be applied with permuted block size to maintain blindness and balance. Subjects will be stratified based on C1-C3 AIS A to ensure equal allocation of those with the most severe respiratory impairment and unlikely to wean from the vent. In our experience, C1-C3, AIS A was associated with lower vital capacity at admission. The study research assistant will randomize subjects in the redcap database, and he/she will not be involved in data analysis.

Blinding: The principal investigator (PI), statistician, outcome assessors, and participants will be blinded to tidal volume assignment.

Study Visits and Procedures:

Screening: Patients will be screened at the time of admission to TIRR Memorial Hermann. Respiratory therapist and SCI attendings will notify PI or research assistant (RA) regarding admits of an SCI patient dependent on mechanical ventilation or cervical SCI patients who are not dependent on MV (controls). PI or RA will discuss eligibility with respiratory therapists or attending physicians. PI may review discharge summary from acute care hospital or history and physical performed at TIRR admission to determine eligibility. If a person doesn't meet eligibility criteria, we will not save any identified data other than deidentified information on the reason for screening failure.

The screening will require information on age, past medical and surgical history, the duration of SCI, etiology of SCI, the dependence on a ventilator, neurological level and current medications.

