11. SAMPLE SIZE AND STATISTICAL METHODS

Determination of Sample Size:

The purpose of the proposed pilot trial is to test the feasibility of conducting a randomized control trial comparing high vs. low Vt MV. Given the complexity of this study and practice variation, it is essential to evaluate recruitment and study procedures. Our cohort study data suggest that approximately 19 patients per year will meet eligibility. Based on Fenton et al. study comparing high vs. low Vt MV in SCI, we anticipate a total recruitment rate of 80% (i.e., that 80% of the eligible would consent for the study), i.e., on average, we are expecting to enroll at least 10-12 participants with SCI who are on mechanical ventilation per year for mechanical ventilation group and total of 30 subjects for 3 years.

For the control group, we will recruit cervical SCI (neurological level C1-C5) who are not dependent on mechanical ventilation at admission to our acute inpatients rehabilitation facility. We plan to recruit a total of 15 subjects in 2 years. This is a pilot study based on feasibility of completing study within the above time frame this sample size was determined. We will have atleast 15 subjects in each group for the analysis.

Statistical and Analytical Plans:

Baseline data and unadjusted analysis of outcome variables will be presented as mean with standard deviation (SD) for a continuous variable with normal distribution otherwise as median with interquartile range (IQR). Categorical and ordinal data will be reported as totals and frequencies for baseline data and unadjusted analysis of outcome variables.

Aim 1: Respiratory outcomes: We will report relative risk with credible interval and posterior probability. We will use neutral prior, and for binary outcomes, this will be centered at RR of 1 with 95% credible interval of 0.3 to 3. Bayesian inference combines a prior or an estimated effect distribution based on previous studies and likelihood, which summarizes findings from the present study.³⁵ All Bayesian analyses will use similar models as the frequentist analyses. We will report risk ratios with 95% credible intervals and posterior probability of benefit or harm associated with the intervention.

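### The mandatory interim stopping rule for pneumonia gives no scale, direction or required certainty, leaves the compared groups unclear, and does not say how tidal-volume blinding survives the look

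*Combined protocol and SAP*

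**What the plan says.** Section 9 (Safety Monitoring Plan) provides for one look: "statistical analysis on rates of morbidity of study participants compared to controls by the PI and the statistician at 50% recruitment stage". The next sentence is the rule: "If preliminary results suggest the risk of pneumonia is <25% in one group compared to another group, we will stop the study".

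Sections 3 and 5 plan three groups of 15: low Vt, high Vt, and controls who are not ventilator-dependent. Only the first two are randomised: "A 1:1 allocation ratio will be applied to the mechanical ventilation groups".

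Section 5 states: "Participants, principal investigator, outcome assessors, and statistician will be blinded to tidal volume assignment". Section 6 (Blinding) repeats this: "The principal investigator (PI), statistician, outcome assessors, and participants will be blinded to tidal volume assignment". Neither makes an exception for the interim look. Section 6 (Randomization) adds: "The study research assistant will randomize subjects in the redcap database, and he/she will not be involved in data analysis".

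For Aim 1, section 11 describes a neutral prior on the risk ratio (RR): "this will be centered at RR of 1 with 95% credible interval of 0.3 to 3". It continues: "We will report risk ratios with 95% credible intervals and posterior probability of benefit or harm associated with the intervention". Section 2 sets a probability above 70% for Hypothesis 1. Neither item is linked to the interim look.

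**The concern.** A rule that obliges the trial to stop should give the same answer to anyone who applies it to the same data. This one leaves four things open.

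- **Scale.** It could mean an RR below 0.25, a risk more than 25% lower in relative terms, a gap of more than 25 percentage points, or one group under 25% while the other is not.
- **Direction.** It does not say which group must be lower.
- **Certainty.** The only evidential standard is that preliminary results suggest the condition.
- **Groups.** The sentence before the rule compares participants with controls, whereas the rule refers to two unspecified groups out of three. Controls are not ventilated and stand outside the 1:1 allocation, so a stop on that contrast would not inform the Vt question.

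The look is also given to the two roles that sections 5 and 6 keep blinded. What is at stake is a feasibility pilot that could end half-way by chance, or on a reading chosen after the data are seen.

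**Working it through.** The plan states no error rate or stopping probability for this rule, so there is no figure to reproduce. The check asks whether plausible readings lead to different decisions.

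**Inputs.** Section 3 plans 30 ventilated subjects, and half is 15, taken as 7 versus 8. Section 9 does not say what total its 50% refers to, so this is an assumption. The documents give no pneumonia risk, so a common true risk p of 10% to 80% is assumed.

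**Readings.** With a events among 7 and b among 8, let lo and hi be the smaller and larger of a/7 and b/8. All signs are strict, and either arm may be the lower one.

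- R1: lo/hi < 0.25
- R2: lo/hi < 0.75 (relative difference above 25%)
- R3: hi − lo > 0.25
- R4: lo < 0.25 and hi ≥ 0.25

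**Counting tables.** There are 8 × 9 = 72 possible results. All four readings stop on 20 and none stops on 18, so they conflict on 72 − 20 − 18 = 34. Two examples:

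- 1/7 vs 4/8: 14.3% vs 50%, RR 0.286, gap 35.7 points. R2, R3 and R4 stop; R1 continues.
- 2/7 vs 4/8: 28.6% vs 50%, RR 0.571, gap 21.4 points. R2 stops; the other three continue.

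**Probabilities with no true effect.** Each table has probability C(7,a) · C(8,b) · p^(a+b) · (1−p)^(15−a−b). Summing over the relevant tables gives, in percent:

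| p | R1 stops | R2 stops | R3 stops | R4 stops | Four readings conflict | R1 and R4 conflict |
|---|---|---|---|---|---|---|
| 10% | 49.8 | 62.8 | 9.5 | 28.1 | 54.4 | 46.9 |
| 20% | 32.2 | 69.7 | 19.7 | 49.9 | 56.8 | 44.1 |
| 30% | 17.0 | 66.3 | 26.0 | 41.7 | 54.8 | 30.8 |
| 40% | 9.2 | 62.1 | 29.2 | 23.1 | 53.9 | 14.8 |
| 50% | 4.7 | 57.7 | 30.2 | 9.3 | 53.2 | 4.7 |
| 80% | 0.0 | 26.9 | 19.7 | 0.0 | 26.9 | 0.0 |

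The last column takes only the two readings that keep the printed less-than sign. They conflict on 7 tables: 0/7 vs 1/8, 1/7 vs 0/8, 1/7 vs 2/8, 1/7 vs 3/8, 1/7 vs 4/8, 2/7 vs 1/8 and 3/7 vs 1/8. At p = 10% the two single-event tables contribute 15 × 0.1 × 0.9^14 = 34.3 points and the other five 12.6, together 46.9.

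**Would the section 11 RR settle it?** Take 1/7 vs 4/8 and a log-RR prior centred at 0.

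- Normal approximation: ln RR = ln(0.286) = −1.253, with variance 1 − 1/7 + 1/4 − 1/8 = 0.982. A prior SD of ln 3/1.96 = 0.561 (variance 0.314) gives posterior mean −1.253 × 0.314/(0.314 + 0.982) = −0.304 and SD 0.488. So Pr(RR<1) = Φ(0.304/0.488) = 0.73. With prior SD (ln 3 − ln 0.3)/3.92 = 0.587 it is 0.74.
- Exact binomial likelihood, prior SD 0.561: 0.86 with a flat prior on the risk in the 4/8 arm, 0.75 with a flat prior on the risk in the 1/7 arm, and 0.81 to 0.83 with a flat prior on the geometric mean of the two risks.

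Section 11 states neither the likelihood nor the baseline-risk prior, so the same result gives about 0.73 to 0.86.

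**Blinding, side by side.** Section 9 assigns the look to the investigator and statistician; sections 5 and 6 blind both to Vt assignment. The masking in section 8 covers event adjudication and the biomarker assessor, not this look. A comparison of Vt arms by identity breaks the blind. A comparison of pooled ventilated patients with controls does not. The plan does not say which is meant.

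**The case against.** Several counter-arguments carry weight.

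- **The figures depend on the readings.** R2 and R3 turn the printed less-than sign into a difference greater than 25%. With R1 and R4 alone, conflict falls from 34 tables to 7 and is rare at higher risks. This stands. A reader might take 53–57% as the measured chance of an inconsistent decision; it is only an illustration, on assumed risks and an assumed interim size.
- **The preceding sentence does name a comparison.** This stands in part. It names participants versus controls, but the rule does not repeat it, and that contrast does not address tidal volume.
- **Unblinding is not certain.** A reader might infer that the look must unblind the investigator and statistician. The documents do not support that, because a pooled comparison would not.
- **Section 11 supplies an RR framework.** A reader might infer that adopting it removes the ambiguity, or that an RR threshold of 0.25 applied to a posterior median could never fire. Nothing ties section 11 to this look, R1 does fire on observed risks, and section 11 leaves the model incomplete.
- **It is a feasibility pilot without stated alpha or power.** True, and no particular error rate is demanded of it. But the stop is unconditional, so the rule still has to be applicable.

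**Conclusion.** The concern holds. No other section repairs the missing scale, direction and certainty or settles the pair of groups, and the conflict with the blinding statements is real if the Vt arms are compared by identity.

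That the same data can stop or continue the trial does not depend on any assumed risk: at 7 versus 8, four readings conflict on 34 of 72 results, and the two closest to the printed sign on 7. The probabilities do depend on assumptions (observed risks, strict signs, no true effect, common risk 10–80%). The four readings conflict in 53–57% of trials at 10–50% risk, falling to 27% at 80%. R1 and R4 alone conflict in 47, 44, 31, 15 and 5% at 10, 20, 30, 40 and 50%. The chance of a false stop at 30% risk runs from 17% to 66%.

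This should be fixed before the look is taken.

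**What to change.** Reconcile sections 5, 6, 9 and 11.

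1. State that the stopping comparison is between the two randomised Vt arms, and report controls descriptively.
2. State one criterion with its scale, direction and required certainty. If it uses the section 11 Bayesian RR, state the full model: likelihood, baseline-risk prior and log-RR prior. The sponsor should choose the cut-off after tabulating false-stop and detection rates at the interim size.
3. Have the person who holds the allocation supply the interim data as arms A and B, use a symmetric criterion, and withhold Vt and ventilator settings from the interim data of the investigator and statistician. Coding alone does not secure masking: section 6 lists Vt among the collected data, and section 10 gives the investigator access to the database and review of anomalies. If withholding is not practicable, state that these two roles are unblinded at this look.

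The cost is about a paragraph in the monitoring plan, a short calculation and a restricted data export, with no extra patients. The downside is that the trial may stop less readily on small early differences, and coded arms still reveal the size of the difference.
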